8. TRIAL TREATMENT

8.1. Trial Intervention and Comparator

Eligible patients will be offered participation in the COMBAT study. If they consent, they will be randomised (1:1) to the intervention or comparator group.

Intervention: Phacovitrectomy

Participants will undergo phacovitrectomy to remove the lens (phacoemulsification and intraocular lens implantation) and to repair the RRD (vitrectomy). Based on the BEAVRS database, most vitreoretinal surgeons in the UK are not currently undertaking combined phacovitrectomy for RRD. Phacovitrectomy, however, is common practice for other retinal disorders such as macular hole. Although a phacovitrectomy is done in the same manner whether the condition to be treated is macular hole or RRD, the calculations required for the surgeon to select which intraocular lens should be implanted are different if there is a RRD with a detached macula. For this reason, a Standard Operating Procedure (SOP) will be prepared for the phacovitrectomy group to guide surgeons on how to best determine the intraocular lens under these circumstances (17). Vitrectomy with any gauge size (e.g.23g, 25g, 27g) will be allowed for the surgery, as per standard care at the participating site. The choice of the tamponade agent will be at the discretion of the treating vitreoretinal surgeon, as per standard care.

Comparator: Vitrectomy (Standard Care)

Participants will receive vitrectomy to repair their RRD. The vitrectomy would be done as per standard care. Vitrectomy with any gauge size (e.g.23g, 25g, 27g) will be allowed for the surgery, as per standard care at the participating site. The choice of the tamponade agent will be at the discretion of the treating vitreoretinal surgeon, as per standard care. Then, if a cataract develops, phacoemulsification and intraocular lens implantation will be done as per standard clinical practice.

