Rates of PCO and of YAG posterior capsulotomy will be analysed as per categorical outcomes by using GLM with adjustment for minimisation covariates. Relative risk, risk difference and odds ratio will be reported, where possible. We will undertake a sensitivity analysis on the basis of the performance (or not) of an intraoperative capsulectomy, if numbers allow, to explore the potential effect on outcomes of this manoeuvre. Participants will be consented for COMBAT researchers to review their medical records and establish contact with their optometrist to gather information about whether participants in the vitrectomy only arm receive cataract surgery and, if they do, whether YAG-

capsulotomy is undertaken after the trial ended. These data will be used to provide long-term outcomes with regard to cataract surgery, refractive error, and rates of YAG-posterior capsulotomy.

Missing Data

Every effort will be made to minimise missing baseline and outcome data and data queries will be generated for site staff as required to request missing information.

Standard approaches will be used to detect patterns in missing data. The level and pattern of the missing data in the baseline variables and outcomes will be established by forming appropriate tables and the likely causes of any missing data will be investigated. This information will be used to determine whether the level and type of missing data has the potential to introduce bias into the analysis results for the proposed statistical methods, or substantially reduce the precision of estimates related to treatment effects. We plan for the principal analysis to be based upon available case data with no imputation of missing values. Sensitivity analyses will be undertaken to assess the impact of missing data by imputing extreme values (lowest and highest), as stated above.

A detailed Statistical Analysis Plan (SAP) will be prepared and made publicly available before undertaking the final analysis.

Analysis of Quality of Life Data

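### Post-trial YAG capsulotomy is sought only in the vitrectomy arm, so the promised long-term YAG rates have no randomised comparator

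*Protocol*

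**What the plan says.** Protocol section 14.2 (Data Analysis, Statistical Methods) covers posterior capsule opacification (PCO) and YAG capsulotomy in two steps.

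- **Within the trial.** "Rates of PCO and of YAG posterior capsulotomy will be analysed as per categorical outcomes by using GLM with adjustment for minimisation covariates", and "Relative risk, risk difference and odds ratio will be reported, where possible". The one sensitivity analysis attached to this concerns capsulectomy at the index operation: "We will undertake a sensitivity analysis on the basis of the performance (or not) of an intraoperative capsulectomy, if numbers allow". Section 12.4 has PCO and YAG recorded prospectively in the CRF with no restriction by arm, and section 12.1 follows all participants to week 52.
- **After the trial.** Participants consent to review of their records and contact with their optometrist. The stated purpose is to "gather information about whether participants in the vitrectomy only arm receive cataract surgery and, if they do, whether YAG" laser treatment follows; the time in view is given by the words "capsulotomy is undertaken after the trial ended". The stated use comes next: "These data will be used to provide long-term outcomes with regard to cataract surgery, refractive error, and rates of YAG-posterior capsulotomy".

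On lens implantation, section 8.1 says of the intervention arm: "Participants will undergo phacovitrectomy to remove the lens (phacoemulsification and intraocular lens implantation) and to repair the RRD (vitrectomy"). In the comparator arm, lens surgery follows only if a cataract develops.

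**The concern.** The post-trial question is put only for the vitrectomy arm, and within it only for those who have cataract surgery. Yet the arm in which every eye should be implanted from the outset, and in which long-term capsulotomy is therefore most widely relevant, is phacovitrectomy. No collection of YAG data after week 52 is described for it.

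Two things are at stake. First, a randomised trial would report long-term YAG rates with nothing randomised to set them against. Second, the only phacovitrectomy figure available to a reader would be the 52-week one. Putting the two side by side lets events accrue in one arm after they have stopped being counted in the other. An analysis plan can choose denominators and models, but it cannot supply data that nobody was asked to collect.

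**Working it through.** **Plan's own figure.** The protocol states no YAG rate, no cataract-surgery rate in the comparator arm and no length of post-trial review. There is nothing to reproduce, and the calculation below is an illustration.

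**Inputs**
- Phacovitrectomy: implant at time 0 (section 8.1).
- Vitrectomy: implant in 48% or 80% of eyes. These anchors come from section 4.1: 320/664 = 48% had a cataract or had it removed within three months, and 20% had a clear natural lens at 12 months, leaving 80%. Both include cataracts not yet removed, so actual implantation may be lower.
- Assumed: implant dates uniform over months 3 to 12, and a YAG hazard h of 0.05, 0.10 or 0.20 per implanted eye-year, constant and equal in both arms.
- Assumed post-trial horizons T: 24, 36 and 60 months from index surgery.

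**Formulas** (T in years)
- Phacovitrectomy risk: 1 − exp(−hT).
- Vitrectomy risk, with proportion p implanted: p × {1 − [exp(−h(T − 1)) − exp(−h(T − 0.25))] / (0.75h)}.

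**Worked case: h = 0.10, T = 3, p = 0.80**
- Phacovitrectomy at 1 year: 1 − exp(−0.10) = 9.5%; at 3 years: 1 − exp(−0.30) = 25.9%.
- Vitrectomy at 3 years: 0.80 × {1 − [exp(−0.200) − exp(−0.275)] / 0.075} = 0.80 × (1 − 0.789) = 16.9%.
- Same horizon in both arms: 25.9/16.9 = 1.53. Phacovitrectomy stopped at week 52: 9.5/16.9 = 0.56.

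**Results at h = 0.10** (risk ratio is phacovitrectomy over vitrectomy; paired entries are 48% and 80% implanted)

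| T (months) | Phaco at 12 months | Phaco at T | Vitrectomy at T | Ratio, both arms to T | Ratio, only vitrectomy to T |
|---|---|---|---|---|---|
| 24 | 9.5% | 18.1% | 6.2%, 10.3% | 2.94, 1.77 | 1.55, 0.93 |
| 36 | 9.5% | 25.9% | 10.1%, 16.9% | 2.56, 1.53 | 0.94, 0.56 |
| 60 | 9.5% | 39.3% | 17.0%, 28.3% | 2.31, 1.39 | 0.56, 0.34 |

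Over h = 0.05 to 0.20, the ratio with only the vitrectomy arm followed to 36 months is 0.91 to 1.00 (48%) or 0.54 to 0.60 (80%). With both arms followed it is 2.49 to 2.59 or 1.49 to 1.56.

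**What drives the distortion.** The vitrectomy risk cancels when the one-arm ratio is divided by the two-arm ratio, leaving [1 − exp(−h)] / [1 − exp(−hT)]. Over h = 0.05 to 0.20 this is 0.51 to 0.55 at 24 months, 0.35 to 0.40 at 36 and 0.22 to 0.29 at 60. The shrinkage thus depends on the phacovitrectomy hazard and the horizon. The implantation pattern decides only where the ratio starts, and so whether it crosses 1.

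**The case against.** **No long-term comparison is planned.** Section 14.2 says only that the data will provide long-term outcomes. It describes no test between arms and no pooling with week-52 data. A reader might infer from the table that a planned analysis reverses direction. The document does not support that: the change of sign belongs to a comparison it never states, and with 48% implanted it does not occur at 24 months. Nor does section 14.2 say that these rates will enter the long-term economic model, which is conditional and to be supplemented from the literature and expert opinion. This objection stands. It leaves the missing comparator untouched.

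**The within-trial analysis is sound.** A reader might also infer that the 52-week PCO and YAG comparison is distorted by unequal follow-up. It is not. Both arms are followed for 52 weeks from index surgery, with the same recording. Time with an implant does differ: 1.00 year per phacovitrectomy eye against 0.48 × 0.375 = 0.18 to 0.80 × 0.375 = 0.30 year per randomised vitrectomy eye. But delayed or absent implantation is part of the comparator strategy, so the comparison per randomised participant validly contrasts the two strategies. It would mislead only if read as risk per implanted eye or as lifetime burden. Handling of exposure can be left to the analysis plan.

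**The illustration is simple.** Section 12.4 allows capsulectomy during phacovitrectomy by surgeons who do it routinely, and those eyes may not carry the same YAG risk. The calculation also stops cataract surgery at month 12, although the review exists partly to find later operations. Both points affect the levels in the table. Later cataract surgery does not affect the shrinkage factor, because the vitrectomy risk cancels.

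**Importance.** PCO and YAG rates are not named separately among the secondary outcomes in section 10.2. The primary outcome, sample size and equivalence conclusion are unaffected. That is correct.

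**Conclusion.** The point holds as a gap in post-trial ascertainment. The protocol promises long-term YAG rates but describes collecting the data in the vitrectomy arm alone, so those rates have no randomised comparator. If they were set beside 52-week phacovitrectomy rates, the comparison would be biased against the vitrectomy arm. Under a constant, equal hazard of 5% to 20% per implanted eye-year, the risk ratio would fall to roughly half its equal-follow-up value at 24 months and to 0.22 to 0.29 of it at 60. These sizes rest on an assumed hazard and horizon, and the ratios themselves also on assumed implantation; the protocol fixes none of the three. It is a modest point about a descriptive long-term outcome, worth settling because the remedy is cheap and a later analysis plan cannot replace data never sought.

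**What to change.** Reword the post-trial sentence in section 14.2 so that record and optometrist review covers YAG capsulotomy in participants of both arms, either over the same period from index surgery or to one common cut-off date, and state which. The search for later cataract surgery can stay specific to the vitrectomy arm.

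Keep the 52-week comparison per randomised participant as the contrast of strategies. YAG rates by time since lens implantation may be added as a supportive description. They should be labelled non-randomised, because they condition on having had lens surgery, and should identify eyes with intraoperative capsulectomy. No post-trial refraction is needed in the phacovitrectomy arm, since section 10.2 defines its refractive error at week 12.

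**Cost:** record or optometrist checks for up to about 276/2 = 138 more participants, and one extra table if the supportive rates are reported. Consent to record review (section 14.2) and to later use of routine data (section 11.1) is worded for participants generally. The sponsor should confirm that the consent form does not confine the review to the vitrectomy arm.

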10. OUTCOME MEASURES

10.1. Primary Outcome Measure

Change in Best-Corrected Visual Acuity (BCVA) in the affected study eye from baseline to 52 weeks (+/- 6 weeks) after surgery (equivalence margin +/- 7 ETDRS letters).

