14. STATISTICAL CONSIDERATIONS

14.1. Sample Size

COMBAT is powered to demonstrate treatment equivalence for the primary outcome. Based on two one-sided t-tests at the 2.5% significance level, a 15.2-letter standard deviation (27) and an equivalence margin of +/- 7 ETDRS letters (with a difference of 7 or fewer letters being considered not clinically meaningful) (28,29), 248 participants would be required to be 90% sure the 95% confidence interval will exclude a difference in means of more than 7 ETDRS letters. Allowing for 10% dropout, we will require a minimum of 276 participants. This sample size will be sufficient to detect a difference of 16% in the rate of retinal reattachment surgery between groups, which is clinically relevant.

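### The one missing-data sensitivity analysis named for the primary outcome imputes unspecified extreme values, which makes it a poor robustness check against a 7-letter margin

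*Protocol*

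**What the plan says.** The primary outcome is "Change in Best-Corrected Visual Acuity (BCVA) in the affected study eye from baseline to 52 weeks (+/- 6 weeks) after surgery" (Protocol 10.1). Equivalence is concluded if the 95% CI for the difference, from an analysis of covariance adjusted for baseline acuity and the minimisation factors, lies wholly within ±7 letters (14.2, Statistical Methods).

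On missing data, section 14.2 plans for the "principal analysis to be based upon available case data with no imputation of missing values". It then adds: "Sensitivity analyses will be undertaken to assess the impact of missing data by imputing extreme values (lowest and highest), as stated above". The section also promises tables of the level and pattern of missing data, an inquiry into likely causes, and a detailed SAP before the final analysis.

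Nothing above that sentence describes an extreme-value imputation. The two other clinical sensitivity analyses in 14.2 concern surgery more than three days after baseline and intraoperative capsulectomy, and neither is about missing data. The sensitivity analysis on imputation methods later in 14.2 belongs to the economic evaluation.

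Masked, fully refracted acuity is also measured at weeks 6 and 12 (12.1 and 12.4). Neither the available-case analysis nor the extreme-value imputation uses it.

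**The concern.** An equivalence claim should survive plausible departures from the missing-data assumption, and a sensitivity analysis should show how large a departure overturns it. Imputing the lowest and highest values gives a natural bound for a yes/no outcome. For a letter change it puts about a tenth of each arm at the edge of a wide scale, while the margin is only 7 letters.

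The sentence can be read in at least two ways: opposite extremes in the two arms, or the same extreme in both. The extremes could come from the chart or from the observed data. These choices can give opposite answers on one dataset, and as written the choice could be made after the data are seen.

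The available-case analysis conditions only on baseline acuity and the minimisation factors. If dropout depends on early postoperative vision, it can be biased. The week 6 and week 12 measurements that could reduce this bias go unused.

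**Working it through.** **Inputs from the Protocol (14.1, 14.2, 6.1).** SD 15.2 letters; margin ±7; two one-sided tests at 2.5%; 1:1 allocation; 248 evaluable; 276 randomised after 10% dropout, so 138 per arm. A true difference of 0 is implied, not stated.

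**Reproducing the plan's figures.** Per arm, n = 2 × [15.2 × (1.960 + 1.645) / 7]² ≈ 122.5, so 123, or 246 in total. With the t distribution, power is 0.898 at 123 per arm and 0.901 at 124, which gives 248. Then 248 / 0.90 = 275.6, so 276. Both figures reproduce. The planned half-width is 1.96 × 15.2 × √(2/124) = 3.8 letters.

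**Assumed inputs.** The Protocol gives no range for the change in acuity. R is the highest minus the lowest imputed value, and d is the distance of an imputed value from the mean. Both are assumptions. R = 55 is the gap between the 24-letter stratum boundary (9.1) and the 79-letter example (12.4); R = 76 is 5 × 15.2; R = 100 is an upper case.

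**Opposite extremes, fraction f = 0.10 missing in each arm.** Shift = f × R. Variance per arm = 0.9 × 15.2² + 0.09 × d², with d = R/2. An even split about the mean is the mildest case, because for fixed R the sum of the two squared distances is then smallest. Half-width = 1.96 × √(2 × variance / 138). At an observed difference of 0:

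| R | Shift | Half-width | 95% CI |
|---|---|---|---|
| 34 | 3.4 | 3.6 | −0.2 to 7.0 |
| 55 | 5.5 | 3.9 | 1.6 to 9.4 |
| 76 | 7.6 | 4.3 | 3.3 to 11.9 |
| 100 | 10.0 | 4.9 | 5.1 to 14.9 |

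An observed difference of 0 is the most favourable case for passing in both directions. Any other value D adds 0.9 × |D| to the shift in one of them.

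**Same extreme in both arms, 10% missing in each.** The difference becomes 0.9 × D, and the variance formula is unchanged.

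| d | SD | Half-width | Largest \|D\| that still passes, (7 − half-width)/0.9 |
|---|---|---|---|
| 40 | 18.8 | 4.4 | 2.9 |
| 60 | 23.1 | 5.4 | 1.7 |
| 70 | 25.5 | 6.0 | 1.1 |

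The half-width reaches 7 only at d of about 86.

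**Same extreme, 5% v 15% missing.** Shift = (0.15 − 0.05) × d, which is 4.0 letters at d = 40 and 7.0 at d = 70. The upper limits are 8.4 and 13.0.

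**Simulation** (4,000 runs per case; true difference 0; normal changes with SD 15.2; 138 randomised per arm; unadjusted comparison). The chance of showing equivalence was:
- Available cases: 0.91.
- Opposite extremes, one direction: 0.00 to 0.11. Both directions: 0.00. This holds for R of 55 to 100 and for extremes taken from the observed data.
- Same lowest value, balanced dropout: 0.86 (d = 40), 0.62 (d = 60), 0.40 (d = 70), and 0.83 with the observed minimum.
- Same lowest value, random dropout averaging 10%: 0.74, 0.42, 0.25 and 0.69 in the same order.

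**The case against.** The strongest reply is that this is a deliberate stress test, that no decision rule depends on it, and that its details belong in the promised SAP. Much of that stands. The equivalence conclusion rests on the 95% CI from the analysis of covariance, and failing an extreme bound does not overturn it. The Protocol also commits to examining the missing-data pattern and does not rule out further analyses. The sentence covers outcomes in general, including binary ones such as reattachment, for which extreme values are reasonable.

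A reader might infer that the check must fail whatever the data show. The text does not support that: with the same extreme in both arms and balanced dropout, a small observed difference passes. A reader might also take the baseline acuity strata as evidence of a 70-letter range of change. Those strata describe baseline level, and their cut-points (24 and 69) lie 45 letters apart, so every range of change used here is an assumption. The fair comparator is the planned 248 evaluable participants, not 276 with complete data. Baseline adjustment would alter the half-widths somewhat but would not remove the shift.

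The deferral to the SAP does not fully answer the point. The Protocol has already chosen the method and supports it with a cross-reference that leads nowhere.

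**Conclusion.** The point holds as a weakness of the robustness check. With opposite extremes and 10% missing per arm, an imputed range above about 34 letters takes at least one direction past the margin almost regardless of the data. With the same extreme and balanced dropout, the check pulls the difference towards zero and widens the interval from 3.8 to about 4.4–6.0 letters (d assumed 40–70), so it can pass or fail. With 5% v 15% dropout, it moves the difference by 4–7 letters. The Protocol does not say which version applies, and no version uses the masked interim acuity.

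The results rest on the Protocol's SD and dropout rate, on assumed values of R and d, and on normal, unadjusted changes in the simulation. A reader might infer that the trial's main conclusion is at risk. It is not on this ground, because the sample size reproduces and the primary decision rule is untouched.

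**What to change.** For the primary outcome, replace the sentence with:

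- Multiple imputation by arm under missing-at-random, using baseline, week 6 and week 12 acuity and the minimisation factors, with cataract-surgery status in the vitrectomy arm only (the lens is removed at the index operation in the other arm). A mixed model on weeks 6, 12 and 52 would be an equivalent choice.
- A delta-adjusted tipping-point analysis applied to each arm separately and then to both, reporting the delta at which the 95% CI leaves ±7. The delta range should be justified in the SAP.

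Keep extreme-value imputation only for binary outcomes, or as a labelled bound that states the source of the extremes and their assignment by arm. Delete the reference to an earlier statement. The cost is a wording change and modest extra programming, with no new data.

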5. STUDY AIM AND OBJECTIVES

5.1. Research Hypothesis

We hypothesise that combined phacovitrectomy will be preferred by patients because it will provide faster visual recovery and obviate the need for a second surgery (the cataract surgery) following RRD repair, and possibly reduce the number of reoperations related to failure to re-attach the retina. The COMBAT PPI Group have highlighted that obviating the need for further cataract surgery should have a positive impact on patients because of the stress and anxiety that occurs before surgical procedures. Phacovitrectomy may reduce the number of visits and admissions to hospital, reducing costs and pressures on the NHS and probably reducing costs to patients such as travel costs and time off work for attending hospital visits. These costs are especially problematic for patients with limited income and the self-employed. Phacovitrectomy may also reduce other health inequalities because if cataract surgery is required after RRD repair, long waiting times for this surgery in the NHS could adversely affect people with lower income who may be unable to achieve visual rehabilitation as quickly as those with higher income who can afford to have their cataracts removed privately.

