12. SCHEDULE OF ASSESSMENTS

12.1. Participant Schedule

The frequency of assessments and follow up specifically for the trial are detailed in the schedule of assessments in Table 2. The time points are based on the date of surgery which, ideally, should be the same day as the date of randomisation. The schedule defines the timing of assessments necessary for data collection. Participants will be followed until the final follow up assessment at week 52.

Procedures	Baseline/Screening	Day of Surgery	Week 1 (+ 1 week)	Week 6 (+/- 1 week)	Week 12 (+/- 2 weeks)	Week 52 (+/- 6 weeks)
Informed Consent	X					
Confirmation of eligibility	X					
BCVA+	X			X	X	X
Fundus examination	X*		X	X	X	X
Biometry & Focimetry	X					
Aimed refraction~	Χ					
EQ5D-5L, NEI VFQ- 25 Questionnaires	X			X	X	X
ModRUM					X	Х
Patient Cost					X	
Questionnaire						
Acceptability Survey						X
Semi-structured interviews				Х	Х	Х
Randomisation	Х					
Surgical details		X [@]				
Achieved refraction~				X	X	X
Adverse events (including intraoperative and postoperative complications)	Х	X	Х	X	X	X
Completion of Worksheets	X	X	X	X	X	X

Table 2. Schedule of Assessments

- + At week 1, visual acuity will be measured as per standard clinical practice by a non-masked member of the team. At all other visits (baseline, week 6, week 12 and week 52) full refracted BCVA will be obtained by an optometrist who is masked to the patient's allocation.
- * Recording the following characteristics of the RRD: macula on/macula off; extension (number of quadrants affected: 1, 2, 3 or 4); total number of retinal tears present; number of breaks of ≥1 clock hours in size; presence/absence of PVR-C; presence/absence of inferior (from 4:00-8:00 clock hours) retinal tears in detached retina; [®] = Characteristics of the RRD (as outlined above) to be confirmed (or ruled out) intraoperatively.

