The ModRUM (22) will be used to measure a participant's use of healthcare relating to their eyes. The ModRUM is a validated, concise, generic, measure designed to collect self-report data on the healthcare services people use in UK-based studies Questionnaires will be self-completed by participants with large font questionnaires used when required.

Patient Cost Questionnaire

A questionnaire will measure the out-of-pocket costs to the participant when they attend hospital appointments relating to their eyes and the impact on their ability to work or undertake usual activities. Questionnaires will be self-completed by participants with large font questionnaires used when required.

Participant Experience and Acceptability

A mixed methods evaluation of participant experience and treatment acceptability will be undertaken. This will include serial semi-structured interviews, which will be conducted with a selection of participants from participating sites across all UK nations, at week 6, 12 and 52 post-surgery. Serial interviews will allow us to explore different facets of participant experience and variation over time, to cross-check information received at different interview sittings, and to understand how perceptions change and are recalled (or are re-constructed) for individual participants over time. Participants will be purposefully selected from both randomised groups on the basis of key demographic variables (including Date of Birth, Sex at birth, Sexual Orientation, Ethnicity, Preferred Language, Family Context, Socio-economic Status (e.g. Employment Status, Education level) and post code. Sample size will be determined by data saturation, but for adequate diversity in key characteristics across sites, we estimate interviewing approximately 20 participants, at 3 (maximum) time points each. The interview schedule will be informed by input from the COMBAT PPI group and will be designed to explore/identify:

- i. Participant experiences of treatment over time, and factors influencing these experiences.
- ii. Treatment characteristics, consequences and outcomes that are important to participants, and how these vary over time.
- iii. Participant perceptions about the impact of treatment on their quality of life, including influences on physical, social, and emotional functioning, relationships, employment, civic and recreational activities.

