A within-trial cost-utility analysis will estimate the 52-week cost-effectiveness of phacovitrectomy compared with vitrectomy and subsequent cataract surgery. Current guidelines for conducting (33.34) and reporting (35) economic evaluations will be followed. A NHS and Personal Social Services perspective will be used for the base-case analysis. A secondary analysis will be undertaken from a broader perspective to include non-healthcare costs (e.g. productivity losses and out of pocket costs). Responses to the EQ-5D-5L (20) at baseline, 6,12 and 52 weeks (+/- 6 weeks) after surgery will be converted into utility scores calculated using the method recommended by NICE (33); at the time of writing this protocol, this is currently a model developed by Hernández Alava et al. (36). QALYs will be calculated using the area under the curve method. A secondary analysis will calculate utility scores and QALYs using responses to the EQ-5D-5L (primary measure) and the Visual Function Questionnaire-Utility Index (VFQ-UI)(37) (secondary measure). The latter uses responses from six items on the NEI-VFQ-25 (21). Health and social service resource use data will be measured from baseline to 52 weeks (+/- 6 weeks) after surgery using both the trial worksheets and the ModRUM (22) and will include, for example, surgery costs, ophthalmology, optometrist and other outpatient visits, and GP and nurse consultations. A study specific Patient Cost Questionnaire will collect nonhealthcare costs to the participant. Unit costs from publicly available sources will be used (e.g. NHS

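### The Patient Cost Questionnaire is scheduled only at week 12, so lost work and activity around later cataract surgery go unobserved in the 52-week broader-perspective cost analysis

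*Protocol*

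**What the plan says.** Four parts of the protocol bear on this.

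- **Horizon and scope (section 14.2, Health Economics Evaluation).** "A within-trial cost-utility analysis will estimate the 52-week cost-effectiveness of phacovitrectomy compared with vitrectomy and subsequent cataract surgery". The base case takes an NHS and Personal Social Services perspective. Then: "A secondary analysis will be undertaken from a broader perspective to include non-healthcare costs (e.g. productivity losses and out of pocket costs"). The data source is given as: "A study specific Patient Cost Questionnaire will collect nonhealthcare costs to the participant".
- **Outcome list (section 10.2).** Non-health care costs are a secondary outcome. The list is set at 52 weeks except for items with an asterisk, and this item has none.
- **Instruments (section 12.5).** On the Patient Cost Questionnaire: "A questionnaire will measure the out-of-pocket costs to the participant when they attend hospital appointments relating to their eyes"; it also covers the effect on work and usual activities. No time point or recall period is given there. ModRUM is a different tool, which "will be used to measure a participant's use of healthcare relating to their eyes".
- **Schedule (section 12.1, Table 2).** The Patient Cost Questionnaire has one mark, in the week-12 column. ModRUM has two, at weeks 12 and 52.

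Section 5.1 gives the reason for measuring these costs: phacovitrectomy is expected to reduce visits and admissions, "probably reducing costs to patients such as travel costs and time off work for attending hospital visits".

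**The concern.** The patient-cost benefit expected of phacovitrectomy comes largely from avoiding a second operation. In the comparator arm, cataract surgery follows if and when it is needed, and section 5.1 itself describes long NHS waits for it. Some of these operations will therefore fall between weeks 12 and 52, when the questionnaire is no longer given.

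The gap differs by arm. Costs around the index surgery precede week 12 in both arms and can be reported in both. Cataract surgery after week 12 arises almost only in the comparator. At stake is the broader-perspective analysis: if patient costs stop at week 12, the comparator probably looks cheaper to patients than it is. Section 14.2 also notes that health benefits may prove similar while costs differ, so the cost side could carry much of the conclusion.

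**Working it through.** No stated figure in the plan depends on this point, so the check sets the sections side by side.

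**1. Is the single mark real?** Table 2 ends with the week-12 and week-52 columns. The Patient Cost row has one mark, in the fifth of six visit columns (week 12). The ModRUM row directly above reads intact with marks in both columns. The Patient Cost label is broken over two lines in the extracted text, so a lost week-52 mark cannot be wholly excluded, but the intact neighbouring row makes it unlikely.

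**2. Is there another source for these costs?** Section 14.2 names only this questionnaire for non-healthcare costs. ModRUM and the trial worksheets run to week 52 but cover health and social service use. No section says how patient costs after week 12 are to be obtained.

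**3. What is missing, and what could be rebuilt?** Write the 52-week patient cost in an arm as

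cost(0–52) = cost(0–12) + cost(12–52).

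The second term has two main parts:

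- attendances: number of attendances × out-of-pocket cost per attendance;
- work and activity: number of operations × work and activity lost per operation.

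| Component, weeks 12 to 52 | Count | Cost or loss per event |
|---|---|---|
| Attendances | Available: worksheets and ModRUM to week 52 (14.2) | Could be taken from week-12 answers; not stated |
| Cataract or other eye surgery | Available: number and type of surgeries (12.4) | Not observed for operations after week 12 |

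The first row can be approximated. The second cannot be measured: lost work and activity would have to be imputed from week-12 answers, which reflect the index surgery, early follow-up and any cataract surgery already done by then.

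**4. Can the loss be sized?** Three figures can be formed, and none of them sizes it.

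- Time without the questionnaire: (52 − 12)/52 = 40/52 = 77%. At matching ends of the visit windows: (46 − 10)/46 = 78% and (58 − 14)/58 = 76%. These are shares of calendar time, not of cost; index surgery and the early visits come before week 12.
- Lens status in section 4.1: 320/664 = 48% with cataract recorded or already removed within three months, and 20% with a clear natural lens at 12 months. The difference is (100% − 20%) − 48% = 32%.
- Applied to half of 276 participants: 0.32 × 138 ≈ 44; after the planned dropout, with half of 248: 0.32 × 124 ≈ 40 (39 with the unrounded 320/664).

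The 32% subtracts two different endpoints. An eye with no cataract recorded at three months need not have had a clear lens. It also assumes that both percentages refer to the same 664 eyes, which the wording leaves open. Above all, it counts lens status, not operations. Eyes with a cataract at three months but not yet operated would add later operations, in unknown number. The quantity needed, cataract operations between weeks 12 and 52, is not given.

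**5. Direction.** Comparator cataract surgery pushes the unobserved cost towards the comparator. Other costs after week 12 can arise in either arm: surgery for re-detachment (section 8.2), and YAG capsulotomy (section 12.4), for which every phacovitrectomy participant is at risk from the outset. The net direction is therefore probable, not certain.

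**The case against.** The strongest reply is that the form is tied to attendances. One administration can yield a cost per attendance, to be multiplied by counts that run to week 52. On that view week 12 supplies a unit cost, and the method belongs in the health economic analysis plan that section 14.2 promises before the final analysis. Section 14.2 also foresees sensitivity analyses on imputation methods.

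Much of this stands. It disposes of two stronger readings that a reader might infer. One is that no out-of-pocket costs after week 12 can be estimated; travel and similar costs can be, if the unit-cost approach is adopted. The other is that the hypothesis in section 5.1 cannot be tested; it concerns costs and time off for attending visits, which visit counts and unit costs can at least partly address.

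What remains is the lost work and activity around a cataract operation after week 12. An analysis plan can say how to impute it but cannot supply answers that were never collected. The unit-cost approach is also nowhere stated in the protocol.

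A further reply is that only a secondary analysis is affected. That is correct and limits the weight of the point, but this is a listed secondary outcome and the repair is small.

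**Conclusion.** The point holds in a limited form. Table 2 does not match sections 10.2 and 14.2: a 52-week outcome and a 52-week analysis rest on a questionnaire given once, at week 12. Lost work and usual activity around later cataract surgery would be unobserved. Because that surgery falls almost only on the comparator, using the week-12 data as they stand would probably understate comparator patient costs.

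The size is unknown. It would be tempting to say that 77% of patient costs are missed, or that at least 32% of comparator participants (about 44) have unmeasured surgery costs. The documents support neither: the first counts weeks, and the second counts a change in lens status across two different endpoints and is not a lower bound.

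The conclusion assumes that Table 2 has been read correctly and that some comparator cataract surgery takes place between weeks 12 and 52. The NHS and Personal Social Services base case, the QALYs, the primary outcome and the clinical secondary outcomes are unaffected.

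**What to change.** In Table 2, add the Patient Cost Questionnaire at week 52 beside ModRUM, with recall since week 12 and with items on time off work and lost usual activity for any cataract or other eye surgery in that period. In section 14.2, state that non-healthcare costs combine both periods. If a cost per attendance is also to be applied to visit counts, say so there or in the health economic analysis plan.

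The cost is one more short self-completed form at an existing visit, and an amendment to Table 2 and section 14.2. Recall at week 52 would span about 40 weeks, so the answers will be less exact than those at week 12, but they would observe the loss directly. The change is useful only for participants who have not yet had their week-52 visit, so it should be made early.
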